### 5.3.2 Supportive Care Guidelines for Pneumonitis

Subjects with grade 2 pneumonitis (symptomatic pneumonitis requiring medical intervention) should immediately stop receiving MK-3475 and have an evaluation. The evaluation may include bronchoscopy and pulmonary function tests to rule out other causes such as infection. If the subject is determined to have study drug associated pneumonitis, the suggested treatment plan is detailed in Table 6 and follow-up will be as routine for AEs associated with study drug including monitoring until full resolution of the AEs/pneumonitis.

**Table 6. Recommended Approach to Handling Pneumonitis**

Study drug associated pneumonitis	Withhold/Discontinue MK-3475?	Supportive Care
Grade 1 (asymptomatic)	No action	Intervention not indicated
Grade 2	Withhold MK-3475, may return to treatment if	Systemic corticosteroids are indicated. Taper as indicated.

	improves to Grade 1 or resolves within 12 weeks	
Grade 3 and Grade 4	Discontinue MK-3475	Systemic corticosteroids are indicated.

For Grade 2 pneumonitis that improves to  $\leq$  Grade 1 within 12 weeks, the following rules should apply:

- First episode of pneumonitis
  - May increase dosing interval by one week in subsequent cycles
- Second episode of pneumonitis – permanently discontinue MK-3475 if upon rechallenge subject develops pneumonitis  $\geq$  Grade 2
- Please consult the Events of Clinical Interest and Immune-Related Adverse Events Guidance Document for a more in-depth discussion of pneumonitis.

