#### 4.5 MK-3475 Dosage and Administration

##### Trial Treatments

Drug	Dose/Potency	Dose Frequency	Route of Administration	Regimen/Treatment Period
MK-3475	10 mg/kg	Q2W	IV infusion	Day 1 of each cycle

AEs associated with pembrolizumab exposure may represent an immunologic etiology. These immune-related AEs (irAEs) may occur shortly after the first dose or several months after the last dose of pembrolizumab treatment and may affect more than one body system simultaneously. Therefore, early recognition and initiation of treatment is critical to reduce complications. Based on existing clinical trial data, most irAEs were reversible and could be managed with interruptions of pembrolizumab, administration of corticosteroids and/or other supportive care. For suspected irAEs, ensure adequate evaluation to confirm etiology or exclude other causes. Additional procedures or tests such as bronchoscopy, endoscopy, skin biopsy may be included as part of the evaluation. Based on the severity of irAEs, withhold or permanently discontinue pembrolizumab and administer corticosteroids. Dose modification and toxicity management guidelines for irAEs associated with pembrolizumab are provided in Table 2.

Table 2. Dose Modification Guidelines for Drug-Related Adverse Events

General instructions:				

 
1. Corticosteroid taper should be initiated upon AE improving to Grade 1 or less and continue to taper over at least 4 weeks.
 
2. For situations where pembrolizumab has been withheld, pembrolizumab can be resumed after AE has been reduced to Grade 1 or 0 and corticosteroid has been tapered. Pembrolizumab should be permanently discontinued if AE does not resolve within 12 weeks of last dose or corticosteroids cannot be reduced to <math>\leq 10</math> mg prednisone or equivalent per day within 12 weeks.
 
3. For severe and life-threatening irAEs, IV corticosteroid should be initiated first followed by oral steroid. Other immunosuppressive treatment should be initiated if irAEs cannot be controlled by corticosteroids.
 
				
Immune-related AEs	Toxicity grade or conditions (CTCAEv4.0)	Action taken to pembrolizumab	irAE management with corticosteroid and/or other therapies	Monitor and follow-up

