## 5 GENERAL CONCOMITANT THERAPY AND SUPPORTIVE CARE GUIDELINES

### 5.1 Concomitant Medication

Additional anti-tumor therapies are prohibited during study treatment. Additionally, the use of corticosteroids or other immunosuppressive medications will not be allowed during study therapy (unless used to treat a drug-related adverse event). Low-dose steroid use ( $\leq 10$  mg of prednisone or equivalent) as corticosteroid replacement therapy is allowed.

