### 5.3 Supportive Care Guidelines

Subjects should receive appropriate supportive care measures as deemed necessary by the treating investigator. Suggested supportive care measures for the management of AEs with potential immunologic etiology are outlined along with the dose modification guidelines in Table 2. Where appropriate, these guidelines include the use of oral or IV treatment with corticosteroids, as well as additional anti-inflammatory agents if symptoms do not improve with administration of corticosteroids. Note that several courses of steroid tapering may be necessary as symptoms may worsen when the steroid dose is decreased. For each disorder, attempts should be made to rule out other causes such as metastatic disease or bacterial or viral infection,

which might require additional supportive care. The treatment guidelines are intended to be applied when the Investigator determines the events to be related to pembrolizumab.

Note: If after the evaluation of the event, it is determined not to be related to pembrolizumab, the Investigator does not need to follow the treatment guidance. Refer to Table 2 for guidelines regarding dose modification and supportive care.

It may be necessary to perform conditional procedures such as bronchoscopy, endoscopy, or skin photography as part of evaluation of the event.

Management of Infusion Reactions: Acute infusion reactions (which can include cytokine release syndrome, angioedema, or anaphylaxis) are different from allergic/hypersensitive reactions, although some of the manifestations are common to both AEs. Signs and symptoms usually develop during or shortly after drug infusion and generally resolve completely within 24 hours of completion of infusion. Signs/symptoms may include: Allergic reaction/hypersensitivity (including drug fever); Arthralgia (joint pain); Bronchospasm; Cough; Dizziness; Dyspnea (shortness of breath); Fatigue (asthenia, lethargy, malaise); Headache; Hypertension; Hypotension; Myalgia (muscle pain); Nausea; Pruritis/itching; Rash/desquamation; Rigors/chills; Sweating (diaphoresis); Tachycardia; Tumor pain (onset or exacerbation of tumor pain due to treatment); Urticaria (hives, welts, wheals); Vomiting.

Table 4 below shows treatment guidelines for subjects who experience an infusion reaction associated with administration of MK-3475.

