### 5.3.1 Supportive Care Guidelines for Events of Clinical Interest (ECIs) and Immune-related Adverse Events (irAEs)

Events of clinical interest of a potential immunologic etiology (irAEs) may be defined as an adverse event of unknown etiology, associated with drug exposure and is consistent with an immune phenomenon. irAEs may be predicted based on the nature of the MK-3475 compound, its mechanism of action, and reported experience with immunotherapies that have a similar mechanism of action. Special attention should be paid to AEs that may be suggestive

of potential irAEs. An irAE can occur shortly after the first dose or several months after the last dose of treatment.

If an irAE is suspected, efforts should be made to rule out neoplastic, infectious, metabolic, toxin or other etiologic causes prior to labeling an adverse event as an irAEs. Information on how to identify and evaluate irAEs has been developed and is included in the Immune-Related Adverse Event Guidance Document. Subjects who develop a Grade 2 or higher irAEs should be discussed immediately with the Merck Clinical Monitor.

Recommendations to managing irAEs not detailed elsewhere in the protocol are detailed in Table 5.

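### After a first Grade 2 pneumonitis, Table 6 allows return to treatment without Table 2's steroid condition, and no text says which table governs

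*Combined protocol and SAP*

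**What the plan says.** **Table 2 (Section 4.5).** The pneumonitis row withholds the drug at Grade 2 and gives 1-2 mg/kg prednisone or equivalent, followed by a taper. Two general instructions above the rows apply:

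- Instruction 1: "Corticosteroid taper should be initiated upon AE improving to Grade 1 or less and continue to taper over at least 4 weeks".
- Instruction 2: "pembrolizumab can be resumed after AE has been reduced to Grade 1 or 0 and corticosteroid has been tapered". It continues: "Pembrolizumab should be permanently discontinued if AE does not resolve within 12 weeks of last dose or corticosteroids cannot be reduced to" 10 mg/day or less of prednisone equivalent within 12 weeks.

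**Table 6 (Section 5.3.2).** At Grade 2 the drug is withheld, and the patient may return if the event "improves to Grade 1 or resolves within 12 weeks". Systemic steroids are indicated, to be tapered as the clinician sees fit. The rules below the table address the dosing interval after a first episode and permanent discontinuation after a second. They do not mention steroids.

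**Pointers between the two.** Section 5.3 says: "Refer to Table 2 for guidelines regarding dose modification and supportive care". Section 4.6 (dosing delays) and Section 4.7, item 4 (unmanageable toxicity) also refer to Table 2. For drug-associated pneumonitis, however, Section 5.3.2 says that "the suggested treatment plan is detailed in Table 6". The rules under Table 6 then refer to a separate guidance document on immune-related events, which is not part of these documents.

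**The concern.** The same event carries two restart rules, one with a steroid condition and one without. A reader who goes to the pneumonitis section, as Section 5.3.2 directs, finds a complete-looking rule that depends on grade and time alone.

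The steroid condition has a purpose. Section 5.3 warns that symptoms may worsen as the steroid dose comes down and that several tapers may be needed. Grade 1 on full-dose steroid therefore does not show that the pneumonitis is controlled without it. Re-dosing at that point exposes the patient to the drug again before that is known.

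The general steroid ban in Section 5.1 would not stop such a restart, because it applies "unless used to treat a drug-related adverse event".

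The protocol treats lung toxicity as a particular risk. Section 3.2 excludes current pneumonitis, past pneumonitis that needed steroids, and interstitial lung disease. Section 6.1 requires baseline pulmonary function tests in NSCLC. NSCLC patients make up 44 + 10 = 54 of the 74 planned (Section 11.5).

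**Working it through.** There is no plan figure to reproduce. The check is a comparison of the clauses, followed by the timing that they imply.

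**1. The two rules side by side, first Grade 2 episode**

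| Item | Table 2 | Table 6 |
|---|---|---|
| Initial action | Withhold | Withhold |
| Grade needed to restart | 0 or 1 | 1, or resolved |
| Steroid condition for restart | Tapered | None |
| Start of taper | At Grade 1 or less | Not stated |
| Length of taper | At least 4 weeks | Not stated |
| Stop rule on steroid dose | Cannot reach 10 mg/day or less within 12 weeks | None |
| Start of the 12-week limit on the event | Last dose | Not stated |

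The tables agree that Grade 3-4 pneumonitis, and a recurrence at Grade 2, end treatment. The mismatch is confined to restart after a first Grade 2 episode.

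**2. Does other text supply the missing condition?**

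- Table 5 is for immune-related events not detailed elsewhere, and its steroid limit sits in the Grade 3-4 row. It does not reach Grade 2 pneumonitis.
- Section 5.3.1 requires a discussion ("Subjects who develop a Grade 2 or higher irAEs should be discussed immediately with the Merck Clinical Monitor") but states no restart criterion.
- Sections 4.6, 4.7 and 5.3 refer to Table 2 without saying that it overrides Table 6.

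**3. Timing**

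Let day 0 be the day Grade 1 is reached, and assume an infusion could be given that day. Cycles are 14 days (Section 4.1).

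- Table 6: earliest restart is day 0.
- Table 2, if 'tapered' means the taper is complete: the taper starts on day 0 and lasts at least 4 × 7 = 28 days, so the earliest restart is day 28. The gap is at least 28 days, and 28 / 14 = 2 cycles. Infusions on days 0 and 14 would precede the earliest Table 2 restart, so at least 2. With Table 6's optional extra week between doses they would fall on days 0 and 21, which is still 2.
- Table 2, if 'tapered' means reduced to 10 mg/day or less: the documents do not fix the gap, g. Within a 28-day taper it lies between 0 and 28 days. On the 2-week schedule the number of early infusions is 0 if g = 0, 1 if 0 < g ≤ 14, and 2 if 14 < g ≤ 28.

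The zero end of that range needs a dose already at 10 mg/day or less when Grade 1 is reached. At Table 2's lowest initial dose, 10 mg ÷ 1 mg/kg = 10 kg, so any adult starts above the limit. A zero gap therefore requires the dose to have been lowered before Grade 1, which Table 6's open taper instruction allows.

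**The case against.** The strongest reply is that this is an omission and not a conflict. Table 6 says the patient may return; it does not say that the steroid is irrelevant or that Table 2 is waived. A site that follows Table 2 satisfies both tables. Table 2's general instructions are not limited to particular events, and pneumonitis has its own row there. Three other sections send the reader to Table 2, while Table 6 is headed as a recommendation and introduced as a suggestion. Every immune-related event of Grade 2 or higher must be discussed with the clinical monitor. The guidance document cited under Table 6 may contain the steroid condition.

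Most of this stands, and it limits the weight of the point. It does not close the gap. None of the pointers sets an order of precedence, and the section specific to pneumonitis names Table 6. The monitor discussion is a safeguard without a stated criterion. A condition that one protocol table imposes should not depend on a document outside the protocol.

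A reader might go further and infer that Table 6 authorises restart on full-dose steroid, or that it brings restart forward by a fixed 28 days. The documents support neither. Table 6 is silent on the steroid dose at restart, and 28 days or more follows only if 'tapered' means completed, which Table 2 does not say.

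**Conclusion.** The inconsistency is real and narrow: restart after a first Grade 2 pneumonitis depends on which table the site uses. Under Table 6 alone, re-dosing could come from 0 days to 28 days or more before Table 2 would allow it. On the reduced-dose reading, within a 4-week taper, that is 0 to 2 infusions; on the completed-taper reading it is at least 2.

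These figures assume that an infusion is possible on the day Grade 1 is reached and that the taper starts that day. The documents do not say how many patients would have Grade 2 pneumonitis, so no count of affected patients can be given.

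No sample size, power, error rate or analysis is affected. This is a change to consider, for patient safety and consistent conduct across treating physicians.

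**What to change.** In one amendment:

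1. Replace the Table 6 Grade 2 action with: *Withhold MK-3475; may return to treatment only when Table 2 general instructions 1 and 2 are met (AE at Grade 0-1 and corticosteroid tapered); discontinue permanently per Table 2 general instruction 2.*
2. Add to Section 5.3.2: *Table 2 governs where Table 6 is silent or differs.*
3. Optionally, state once in Table 2 whether 'tapered' means completed or reduced to 10 mg/day or less of prednisone equivalent. The sponsor should choose.

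The 12-week rule should be cross-referenced and not rewritten in Table 6. Table 2 speaks of an event that does not resolve; a paraphrase such as failure to reach Grade 0-1 would create a new mismatch.

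The cost is a few wording edits. The first two add no requirement beyond what Table 2 already contains, and none of them alters the sample size, visit schedule or analysis.

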## 6 STUDY ASSESSMENTS AND PROCEDURES

Systemic treatment with MK-3475 is divided into 2-week cycles, with treatment occurring on Day 1. A window of  $\pm$  3 days can be applied to scheduled visits if necessary for holidays, vacations, inclement weather, etc.

### 6.1 Screening Visit

Prior to initiation of therapy, the patient will require a screening visit. Scans must be done within 28 days prior to the start of systemic therapy; all other evaluations must be completed within 7 days prior to starting MK-3475. At the screening visit, the following will be addressed:

- 1) Informed consent
- 2) History and physical examination
- 3) Measurement of height, weight and vital signs (including blood pressure, heart rate, respiratory rate, oxygen saturation, and temperature).
- 4) Performance status evaluation
- 5) CBC with differential, serum chemistry (Na, K, Cl, CO2, BUN, creatinine, glucose, calcium), magnesium, phosphate, liver function tests (albumin, total protein, alkaline phosphatase, total and direct bilirubin, ALT, AST), LDH, TSH, free T3, free T4
- 6) Plasma and pre-treatment tumor tissue for correlative studies. Melanoma patients are required to have cerebral and extracerebral tissue, unless it is not feasible to obtain the extra-cerebral tissue. Lung cancer patients are required to have extracerebral tissue, unless it is not feasible to obtain the extra-cerebral tissue. If lung cancer patients undergo a surgical resection or biopsy of a brain lesion, they are required to provide a portion of the tissue for research. Plasma can be obtained at screening or any time prior to Cycle 1 Day 1 dosing.
- 7) Pregnancy test (serum or urine) for women of childbearing potential. Sexually active women of childbearing potential must use an effective

method of birth control during the course of the study, in a manner such that risk of failure is minimized.

- 8) Systemic tumor assessment with CT scan of the chest/abdomen/pelvis
- 9) CNS tumor assessment with Brain MRI. MRIs should be done with perfusion, if possible. For patients who will undergo local therapy on trial, investigators must identify “surgical lesion(s)” and “clinically evaluable lesion(s)”. Brain MRI must be done within 28 days of intervention and should be repeated if more than 28 days will have lapsed by the start of systemic therapy. For patients who previously underwent local therapy to a brain lesion and have tumor tissue available for analysis, or those with NSCLC who are not eligible for surgical intervention, only identification of “clinically evaluable lesion(s)” is necessary.
- 10) NSCLC patients will be required to provide a specimen for determination of PD-L1 expression using the assay developed by Merck for entry into Cohort 1.
- 11) NSCLC patients will be required to have baseline pulmonary function tests.

## 6.2 On-Study Visits

Day 1 of each cycle (every 2 weeks):

- 1) History and physical examination
- 2) Measurement of height, weight and vital signs (including blood pressure, heart rate, respiratory rate, oxygen saturation, and temperature).
- 3) Performance status evaluation
- 4) Review concomitant medications; initiation of medications for seizure prophylaxis in patients not on anti-convulsants.
- 5) Adverse events assessment
- 6) CBC with differential, serum chemistry (Na, K, Cl, CO2, BUN, creatinine, glucose, calcium), magnesium, phosphate, liver function tests (albumin, total protein, alkaline phosphatase, total and direct bilirubin, ALT, AST), LDH
- 7) Administration of MK-3475 10mg/kg IV

Day 1 of cycle 3 (after 4 weeks of therapy +/- 5 days)

- 1) Brain MRI to assess patient safety (i.e., to confirm there is no imminent risk in the case of progressing lesion or new/worsening edema). MRIs should be done with perfusion, if possible.

Day 1 every 8 weeks +/- 5 days

- 1) TSH with reflex free T4 and free T3
- 2) Tumor response assessment with:
  - a. CT scan of the chest/abdomen/pelvis
  - b. Brain MRI; MRIs should be done with perfusion, if possible.
- 3) Plasma for correlative studies

**6.3 Follow-up Visits**

All patients who discontinue the study treatment will have a follow up visit at Day 28 ±7 days from the last study treatment.

- 1) History and physical examination
- 2) Measurement of height, weight and vital signs (including blood pressure, heart rate, respiratory rate, oxygen saturation, and temperature).
- 3) Performance status evaluation
- 4) Review concomitant medications
- 5) Adverse events assessment
- 6) CBC with differential, serum chemistry (Na, K, Cl, CO2, BUN, creatinine, glucose, calcium), magnesium, phosphate, liver function tests (albumin, total protein, alkaline phosphatase, total and direct bilirubin, ALT, AST), LDH
- 7) Tumor assessment with CT scan of the chest/abdomen/pelvis and brain MRI with perfusion, if possible, should continue every 8 weeks (+/- 5 days) until progression, withdrawal of consent, death, lost to follow-up, or start of a subsequent anti-cancer therapy

All patients who discontinue early or who complete the study treatment period will be followed for survival. Survival follow-up information will be collected via telephone calls, patient medical records, and/ or clinic visits every 3 months +/- 14 days until death, loss to follow-up or study termination. All patients will be followed for survival unless the patient requests to be withdrawn from follow-up. If the patient withdraws from study treatment but not from follow-up, the study staff may use a public information source to obtain information about survival status.

**6.4 STUDY CALENDAR (Table 7).**

Screening evaluations are to be conducted within 7 days prior to start of systemic therapy. Scans must be done 28 days prior to the start of systemic therapy. In the event that the participant’s condition is deteriorating, laboratory evaluations should be repeated within 48 hours prior to initiation of the next cycle of therapy.

All assessments must be performed prior to administration of any study medication. All study assessments and medications should be administered within ± 3 days of the protocol-specified date, unless otherwise noted.

	Screening Visit	On-Study Visits	Follow-up Visit	Long Term Follow-up
--	-----------------	-----------------	-----------------	---------------------

	Day -28 to -1	Day 1 of each Cycle	Day 1 Cycle 3 (after 4 weeks +/- 5 days of therapy)	Day 1 Cycle 5, and every 8 weeks, thereafter	Day 28 +/- 7 days from last study treatment	Every 3 months +/- 14 days after the follow-up visit
Informed Consent	X					
History/Physical Exam	X	X			x	
Height/Weight/Vital Signs A	X	X			x	
Performance Status	X	X			x	
CBC, serum chemistry, liver function tests, LDH B	X	X			x	
PT/INR (for patients on warfarin)	X	X			X	
Carbamazepine or Phenytoin level (for patients on drug)	X	X			x	
TSH, free T3, free T4	X			x		
NSCLC patients: Determination of PD-L1 expression in tumor (Cohort 1 only)	X					
Plasma for correlative studies	X I			x		
Obtain extracerebral tumor specimen for correlative studies (Refer to Section 6.1 and 9.2)	X					
Pregnancy Test C	x					
CT chest/abdomen/pelvis	x			X D	X E	
Brain MRI	x F		X G	X H	X E	
Selection of "surgical lesion(s)" and "clinically evaluable lesion(s)"	x					
Pulmonary Function Tests – NSCLC patients only	X					
Review concomitant medications		X			x	
Adverse events assessment		X			x	
Administration of MK-3475		X				
Survival Follow-up						X

AIncludes blood pressure, heart rate, respiratory rate, oxygen saturation, and temperature. Height at Visit 1 only.

BIncludes CBC with differential, serum chemistry (Na, K, Cl, CO2, BUN, creatinine, glucose, calcium), magnesium, phosphate, liver function tests (albumin, total protein, alkaline phosphatase, total and direct bilirubin, ALT, AST), LDH

CPregnancy test (serum or urine) is required for women of childbearing potential only.

DCT scan of the chest/abdomen/pelvis should be performed every 8 weeks +/- 5 days of therapy. Response evaluation is performed using RECIST 1.1 and ir-RECIST

ECT scan of the chest/abdomen/pelvis and brain MRI should continue every 8 weeks (+/- 5 days) until progression, withdrawal of consent, death, lost to follow-up, or start of a subsequent anti-cancer therapy

FFor patients who will undergo local therapy on trial, investigators must identify “surgical lesion(s)” and “clinically evaluable lesion(s)”. Brain MRI must be done within 28 days of intervention and should be repeated if more than 28 days will have lapsed by the start of systemic therapy. For patients who previously underwent local therapy to a brain lesion and have tumor tissue available for analysis, only identification of “clinically evaluable lesion(s)” is necessary.

GBrain MRI on Day 1 of Cycle 3 to assess patient safety only; response assessment should not be performed. MRIs should be done with perfusion, if possible.

HBrain MRI should continue every 8 weeks (+/- 5 days) along with systemic evaluation. CNS response evaluation is performed using mRECIST and ir-mRECIST criteria. Perfusion will be done, if possible.

I Can be done at screening or any time prior to Cycle 1 Day 1 dosing

